## Study timeline for the Primary Study Population

## 9.2.2 Study population

The pre-matched study cohort will consist of patients initiating Olodaterol/Tiotropium Bromide or Umeclidinium/Vilanterol between 17 November 2015 and 31 March 2018.

The following exclusion criteria will then be applied:

Aged <40 years.

Enrolment with medical and pharmacy coverage prior to the cohort entry < 180 days.

Never had COPD diagnosis on the cohort entry date or prior to cohort entry.

A record for dispensed Olodaterol/Tiotropium Bromide delivered with Respimat inhalator or Umeclidinium/Vilanterol delivered with the Ellipta Inhaler during the 180-day baseline prior to cohort entry.

[figure not shown]
Diagnosis of asthma any time prior to cohort entry.

Diagnosis of lung cancer any time prior to cohort entry.

Diagnosis of lung transplant any time prior to cohort entry.

Figure 2

Below depicts the flow diagram of patients.

Diagnosis of COPD (ICD-9: 491.\*, 492.\*, 496.\*; ICD-10: J41.0, J41.1, J41.8, J42.\*, J43.0, J43.1, J43.2, J43.8, J43.9, J44.0, J44.1, J44.9) will be defined as the presence of an inpatient or outpatient claim.

Diagnosis of asthma (ICD-9: 493.\*; ICD-10: J45, J45.20, J45.21, J45.22, J45.90\*, J45.99\*) will be defined as either 1 inpatient claim or 2 outpatient events 30-365 days apart.

Diagnosis of lung cancer (ICD-9: 162.2, 162.3, 162.4, 162.5, 162.8, 162.9, 231.2; ICD-10: C34.00, C34.01, C34.02, C34.10, C34.11, C34.12, C34.2, C34.30, C34.31, C34.32, C34.80, C34.81, C34.82, C34.90, C34.91, C34.92, C7A.090, D02.20, D02.21, D02.22, Z85.118) will be defined as either 1 inpatient claim or 2 outpatient events 30-365 days apart.

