as Spiolto in the EU). Anoro® Ellipta®, a combination of Umeclidinium and Vilanterol delivered via dry powder inhaler (DPI), was approved in December 2013 in the US and in February 2014 in the EU. Both products are maintenance therapies consisting of a combination of long-acting muscarinic antagonists (LAMA) and long-acting beta agonists (LABA). However, the question of whether different devices (DPI and SMI) play a role in treatment persistence remains to be answered.

This study seeks to compare the treatment persistence of two drugs in same drug class (LAMA/LABA as a fixed dose combination [FDC]) delivered through different devices (a DPI and a SMI) within an administrative claims database in the US.

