### **9.2 SETTING**

#### **9.2.1 Definitions**

Study Period: the period of time that includes the exclusion criteria assessment period, baseline, cohort entry date, and follow-up period for the study population. This period is the same for all patients.

The study period will be from 1 January 2008 to 31 March 2018, encompassing date of the earliest data availability to the date of the latest data availability.

Patient Selection Period: the period of time for which patients are eligible to enter the cohort. The earliest date of the patient selection period is 17 November 2015, corresponding to 180-days after US approval date of Stiolto Respimat.

Cohort Entry Date: Date of entry to the initial cohort of Stiolto or Anoro users.

[figure not shown]
Baseline Period: the 180-day period that ends 1 day prior to the cohort entry date used to assess covariate information. The baseline period will vary between patients depending on these dates. The earliest start of the baseline period would be 21 May 2015, the date of Stiolto approval (i.e. 180 days before November 17, 2015).

Follow-Up Period: the period of time between 1 day after the cohort entry date to the earliest occurrence of the outcome (discontinuation of refills), or any censoring criteria (365 days, death, disenrollment, or end of data). Addition of another treatment in addition to index treatment will not count as discontinuation.

For entry into the study population, patients will be required to have 180 days of continuous enrolment with both medical and pharmacy coverage. Data during the baseline period will be used to confirm study eligibility and classification of incident COPD. The follow-up period will be used for capturing first and second maintenance therapies. This is illustrated in **Figure 1**.

Figure 1

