**9.4 DATA SOURCES**

The proposed study will utilize data from Truven MarketScan data (US).

The Truven MarketScan databases capture longitudinal, individual-level administrative claims data from the United States. The data available for the study includes three components of MarketScan: the Commercial Claims and Encounters (CCAE) Database, the Medicare Supplemental and Coordination of Benefits Database (MDCR), and the Medicaid Database. Patients in the databases include active employees, dependents, retirees, COBRA recipients, and Medicare or Medicaid enrollees. Data were drawn from large employers, health plans, and public organizations in the United States. The following tables of the MarketScan databases were available for analysis: Enrollment Detail, Inpatient Admissions, Inpatient Services, Outpatient Services, Outpatient Pharmaceutical Claims, and Long Term Care. These tables provide information on plan enrollment, healthcare utilization and expenditures, demographics, and integrated records for inpatient events, outpatient events, and pharmacy dispensings. Data are available from January 1, 2008 to March 31, 2018, and represent approximately 162 million patients.

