## **9.9 LIMITATIONS OF THE RESEARCH METHODS**

This study will be conducted using data from insurance claims and is subject to certain limitations. One limitation is that these are based on a large, non-random convenience sample, which may contain biases or lack generalizability to other populations. Data also come mostly from large employers, and although the database also includes a large amount of data from health plans, data from medium and small firms may be underrepresented.

Additionally, the MarketScan database also poses some limitations inherent to administrative claims data. Electronic outpatient pharmacy dispensing records are considered accurate because pharmacists fill prescriptions with little room for interpretation and are reimbursed by insurers on the basis of detailed, complete, and accurate claims submitted electronically (Sternbach 1988, Levy 2003). Pharmacy dispensing information is usually seen as the gold standard of drug exposure information compared to self-reported information (West 1995) or prescribing records in outpatient medical records (West 1994). However, drugs used during hospital stays are not recorded in this data source. Claims data are subject to certain limitations. The presence of a claim for a filled prescription does not indicate that the medication was consumed or that it was taken as prescribed, and any medications filled over-the-counter or provided as samples by the physician will not be observed in the claims data. Furthermore, as with all claims-based analyses, study results may not be generalizable to the overall population as patients who have commercial health insurance may be different from those with non-commercial or without (commercial) health insurance. Finally, patients are required not to have a claim for Olodaterol/Tiotropium Bromide or Umeclidinium/Vilanterol during the baseline period, but use of these medications may have occurred prior to the start of the baseline period.

In the analytical portion of this protocol, propensity score matching will be used to estimate relative persistence between the two exposures of interest. Various covariates are included in the prediction model of the propensity scores, but as with all non-interventional studies, the potential for unmeasured and residual confounding cannot be ruled out.

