## **ANNEX 5. TABLE SHELLS AND PROPOSED FIGURES**

**Table 1.** Cohort Selection

	Excluded	Remaining
Eligible Population		
Did not meet cohort entry criteria (use of Tio/Olo or Ume/Vi)		
< 180 days of continuous enrollment		
Prior use of Ume/Vi during 180d washout		
Prior use of Tio/Olo during 180d washout		
Tio/Olo and Ume/Vi both occurring on cohort entry date		
Age <40 years		
No prior diagnosis of COPD any time prior using all available data		
Diagnosis of Asthma any time prior using all available data		
Diagnosis of Lung Cancer any time prior using all available data		
Lung Transplant any time prior using all available data		
Final cohort		

**Table 2.** Patient Characteristics of the Study Population (Unmatched/ Matched)

	Tio/Olo	Umech/Vi	Standardized Difference (95% CI)
N			
Median Follow-up Time [IQR]			
Demographics			
Age on index date			
Mean (SD)			
Median [IQR]			
Gender			
Male; n (%)			
Female; n (%)			
Region			
Northeast; n (%)			
North Central; n (%)			
South; n (%)			
West; n (%)			
Missing/Unknown; n (%)			
Insurance Type			
Commercial; n (%)			
Medicare; n (%)			
Missing; n (%)			
Year of Cohort Entry, n (%)			
First Year (November 17, 2015 – November 30, 2016); n (%)			
Second Year (December 1, 2016 – November 30, 2017); n (%)			
Third Year (December 1, 2017 to March 31, 2018)			
Concomitant Medications			

Proprietary confidential information © 2019 Boehringer Ingelheim International GmbH or one or more of its affiliated companies

	Tio/Olo	Umec/Vi	Standardized Difference (95% CI)
Oral Corticosteroids; n (%)			
Short acting muscarinic antagonist (SAMA), n (%)			
Short acting beta agonist (SABA), n (%)			
Long acting muscarinic antagonist (LAMA), n (%)			
Long acting beta agonist (LABA), n (%)			
Inhaled corticosteroid (ICS), n (%)			
LAMA / LABA combination (not Tio/Olo or Umec/Vi), n (%)			
LABA / ICS combination, n (%)			
LAMA / LABA / ICS combination, n (%)			
NSAIDs, n (%)			
Antihistamines, n (%)			
Opioids, n (%)			
Oral antibiotics, n (%)			
Antidiabetic Agents (not including insulin), n (%)			
Insulin (basal or mealtime), n (%)			
Methotrexate, n (%)			
Statins; n (%)			
Antihypertensives; n (%)			
Anticoagulants; n (%)			
Anti-psychotic/anti-depressives/anxiolytic, n (%)			
Oxygen therapy, n (%)			
Comorbidities/Symptoms			
History of All-Cause Hospitalization; n (%)			
History of Emergency Department Visit; n (%)			

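### The new-user washout screens only 180 days of study-drug history, which leaves more unscreened market time for Anoro than for Stiolto

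*Combined protocol and SAP*

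**What the plan says.** Section 9.2.2 excludes a patient with a dispensing of Stiolto or of "Umeclidinium/Vilanterol delivered with the Ellipta Inhaler during the 180-day baseline prior to cohort entry". The attrition shell (Annex 5, Table 1) repeats the rule, "Prior use of Ume/Vi during 180d washout", with a matching row for Stiolto. Required enrolment is also 180 days.

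History is searched much further back for other purposes. Table 1 has "Diagnosis of Asthma any time prior using all available data", and applies the same look-back to COPD, lung cancer and lung transplant. Section 9.4 states "Data are available from January 1, 2008 to March 31, 2018", and 9.2.1 sets the study period to match: "The study period will be from 1 January 2008 to 31 March 2018".

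On timing, section 7 says Anoro "was approved in December 2013 in the US". Section 9.2.1 says: "The earliest date of the patient selection period is 17 November 2015, corresponding to 180-days after US approval date of Stiolto Respimat". It dates that approval to 21 May 2015, which is also the earliest possible start of a baseline period.

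Section 9.9 concedes that "use of these medications may have occurred prior to the start of the baseline period". It does not mention that the opportunity for such use differs between the two drugs.

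**The concern.** A patient who stopped Anoro or Stiolto more than 180 days ago and then fills again counts as an initiator. For a persistence outcome this matters. Such a patient has already tried a study device and gone at least 180 days without a fill, so later persistence may differ from that of someone starting for the first time.

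The washout length is the same for both drugs, but the drugs' histories are not. The selection period was timed so that the earliest washout reaches back exactly to Stiolto's approval. It does not reach back to Anoro's.

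Nothing else in the plan deals with earlier use. The covariates in 9.3.3 come from the 180 days up to entry, and the LAMA/LABA covariate leaves out the two study drugs. Earlier study-drug use is therefore absent from the propensity score and from the multivariable models, which use the same list. None of the four sensitivity analyses in 9.7.2 lengthens the washout. What is at stake is whether part of the hazard ratio for the device comparison reflects different proportions of former users in the two arms.

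**Working it through.** **Inputs.** Stiolto approval 21 May 2015, first entry 17 November 2015 and washout 180 days (9.2.1, 9.2.2); last entry 31 March 2018 (9.2.2); Anoro approval December 2013 (section 7; no day is given, so 1 to 31 December is used as a range); 3,889 Stiolto and 10,862 Anoro initiators (9.5). Market time is counted from approval, because the documents give no launch dates.

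**The plan's own date.** 21 May 2015 + 180 days = 17 November 2015. It reproduces exactly.

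**Unscreened market time at a given entry date.** Formula: (entry date − 180 days) − approval date, floored at zero.

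- Entry 17 November 2015: the washout starts on 21 May 2015. Stiolto: 0 days. Anoro: 506 days (from 31 December 2013) to 536 days (from 1 December 2013), about 17-18 months.
- Sensitivity analysis 3, entry 21 May 2015: the washout starts on 22 November 2014. Stiolto: 0 days. Anoro: 326-356 days.

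The difference of 506-536 days is the gap between the two approvals. It is the same at every entry date in the selection period if the formula is simply run forward.

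**Bound if entry is the first fill in the selection period.** A fill on or after 17 November 2015 would then itself be the entry date or lead to exclusion, so hidden use must precede 17 November 2015. Market time before that date:

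- Stiolto: 180 days.
- Anoro: 506 + 180 = 686 to 536 + 180 = 716 days.

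**Illustration of the effect.** The documents give no count of former users. Let s be an assumed excess share of former users in the Anoro arm, and r their discontinuation hazard relative to true initiators. With a true hazard ratio of 1.00, the apparent Stiolto-versus-Anoro ratio is approximately 1 / (1 − s + s·r).

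| s | r = 0.7 | r = 1.3 |
|---|---|---|
| 2% | 1/0.994 = 1.006 | 1/1.006 = 0.994 |
| 10% | 1/0.97 = 1.03 | 1/1.03 = 0.97 |
| 20% | 1/0.94 = 1.06 | 1/1.06 = 0.94 |

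**Scale against random error.** Assume that every Stiolto patient gets two matches (2 × 3,889 = 7,778) and that 60% discontinue. Neither figure is promised by the plan. The standard error of the log hazard ratio is then √(1/(0.6 × 3,889) + 1/(0.6 × 7,778)) = 0.025. The shift is about a quarter of a standard error at 2%, about 1.2 at 10% and about 2.3-2.4 at 20%.

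**The case against.** The strongest reply is that this is a disclosed design choice. The window is stated, is identical for both drugs, agrees between 9.2.2 and Table 1, and 9.9 admits that earlier use is possible. A washout that defines a fresh treatment episode also need not use the look-back of a diagnosis that establishes disease history. That is fair as far as it goes. It does not answer the inequality between the drugs, which 9.9 leaves out, or the absence of any analysis that tests the window.

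Two stronger readings are tempting, and neither is supported.

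- A reader might infer that the Anoro arm necessarily holds more former users and that the hazard ratio is therefore biased. Time since approval is not use, and the documents give no uptake or restart figures. The washout also leaves former Anoro users free to enter the Stiolto arm as new users, so contamination is not confined to one arm.
- A reader might run the calendar to the last entry date and quote 865 unscreened days for Stiolto against 1,371-1,401 for Anoro. Section 9.2.1 does not spell out the entry rule. On the natural reading that each patient enters once, at the first fill in the selection period, the ceilings are 180 and 686-716 days.

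Zero unscreened time for Stiolto likewise holds only at the first entry date in the selection period, or before it in sensitivity analysis 3.

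It is also true that a longer look-back is only a partial remedy. With 180 days of enrolment required, it finds earlier use only in patients with longer histories.

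**Conclusion.** The point stands as a gap worth closing, not as a demonstrated bias. The documents establish a 180-day screen, data that predate both approvals, 506-536 more days of market time for Anoro, no adjustment for earlier study-drug use, and no sensitivity analysis that changes the washout. They do not establish how many former users there are, how they divide between the arms, or whether they persist better or worse than true initiators.

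The range of about 0.94-1.06 around a true hazard ratio of 1.00 rests wholly on assumed excess shares of 2-20% and hazard multipliers of 0.7-1.3. At the low end the effect is negligible. At the high end it would exceed random error in a cohort of this size, if the assumed matching and event fraction hold. Since the data to settle the question are already available, it is better answered by a count than left as a caveat.

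**What to change.** Add a fifth sensitivity analysis to 9.7.2 that excludes any patient with a dispensing of either study drug at any time before cohort entry, using all available data. Keep 180 days as the minimum enrolment, so that no patient is screened less than now. Report the number removed in each arm, and the results in the formats of Tables 4 and 5. The alternative is to make this the primary criterion in 9.2.2 and Table 1. The sensitivity analysis is the safer course, because look-back would vary between patients with length of enrolment.

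In 9.9, state that the unscreened period is longer for Anoro than for Stiolto. One sentence in 9.2.1 saying whether entry is the first fill in the selection period would settle which bound applies.

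The cost is one criterion and a re-run of the cohort selection, matching and models. The cohort would be somewhat smaller, by an amount that the documents do not allow to be estimated.

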#### 4. Do Not Exclude Patients with Diagnosis of ACOS from the Cohort

Patients in the primary analysis with diagnosis of asthma (regardless of whether or not they have COPD) will be excluded to restrict to patients with only COPD. It is possible that some patients with COPD may have a claim for asthma prior to their COPD diagnosis as part of their COPD diagnostic work-up, rather than an ongoing asthma diagnosis. Therefore, this sensitivity cohort will not exclude patients with a previous diagnosis of asthma. Note that patients with only asthma but no COPD will still be excluded from this cohort.

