History of Hospitalization due to Respiratory Condition	1 Inpatient 
Diagnosis Code (Principal), ICD-9 is any of: { "415.1", "415.11", "415.12", "415.13", "415.19", "465", "465.0", "465.8", "465.9", "466", "466.0", "466.1", "466.11", "466.19", "480.0", "480.1", "480.2", "480.3", "480.8", "480.9", "481", "482.0", "482.1", "482.2", "482.30", "482.31", "482.32", "482.39", "482.40", "482.41", "482.42", "483.0", "483.1", "483.8", "484.1", "484.3", "484.5", "484.6", "484.7", "484.8", "486", "487.0", "488.01", "488.11", "488.81", "490", "491", "491.0", "491.1", "491.2", "491.20", "491.21", "491.22", "491.8", "491.9", "492.0", "492.8", "493.0", "493.00", "493.01", "493.02", "493.1", "493.10", "493.11", "493.12", "496", "515", "516.3", "516.30", "516.31", "516.32", "516.8", "516.9", "518.81", "518.83", "518.84" }
 
Diagnosis Code (Principal), ICD-10 is any of: { "A01.03", "A02.22", "A37.01", "A37.11", "A37.81", "A37.91", "A40.3", "A50.04", "A54.84", "B01.2", "B05.2", "B06.81", "B77.81", "B95.3", "B96.0", "B96.1", "I26.9", "I26.90", "I26.92", "I26.99", "J06", "J06.0", "J06.9", "J09.X1", "J09.X2", "J10.0", "J10.00", "J10.01", "J10.08", "J10.1", "J11.0", "J11.00", "J11.08", "J11.1", "J12", "J12.0", "J12.1", "J12.2", "J12.3", "J12.8", "J12.81", "J12.89", "J12.9", "J13", "J14", "J15", "J15.0", "J15.1", "J15.2", "J15.20", "J15.21", "J15.211", "J15.212", "J15.29", "J15.3", "J15.4", "J15.5", "J15.6", "J15.7", "J15.8", "J15.9", "J16", "J16.0", "J16.8", "J17", "J18", "J18.0", "J18.1", "J18.2", "J18.8", "J18.9", "J20", "J20.0", "J20.1", "J20.2", "J20.3", "J20.4", "J20.5", "J20.6", "J20.7", "J20.8", "J20.9", "J21.0", "J22", "J39", "J39.3", "J39.8", "J39.9", "J40", "J41", "J41.0", "J41.1", "J41.8", "J42", "J43", "J43.0", "J43.1", "J43.2", "J43.8", "J43.9", "J44.0", "J45", "J45.2", "J45.20", "J45.21", "J45.22", "J45.3", "J45.30", "J45.31", "J45.32", "J45.4", "J45.40", "J45.41", "J45.42", "J45.5", "J45.50", "J45.51", "J45.52", "J45.9", "J45.90", "J45.901", "J45.902", "J45.909", "J45.99", "J45.991", "J45.998", "J47.0", "J68.0", "J84.111", "J84.116", "J84.117", "J84.2", }

	“J85.1”, “J96”, “J96.9”, “J96.90”, “J96.91”, “J96.92”, “J96.0”, “J96.00”, “J96.01”, “J96.02”, “J96.1”, “J96.10”, “J96.11”, “J96.12”, “J96.2”, “J96.20”, “J96.21”, “J96.22”, “J98”, “J98.2”, “J98.3”, “J98.8” }

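### The asthma exclusion in Section 9.2.2 omits ICD-10 codes J45.3x, J45.4x and J45.5x, so as written the primary cohort is not restricted to COPD without asthma

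*Combined protocol and SAP*

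**What the plan says.** The exclusion criteria in Section 9.2.2 include "Diagnosis of asthma any time prior to cohort entry". The code definition later in that section opens with "Diagnosis of asthma (ICD-9: 493" followed by a wildcard, so every ICD-9 asthma code counts. The ICD-10 part begins "ICD-10: J45, J45.20, J45.21, J45.22"; in full, with the claims rule, it reads "ICD-10: J45, J45.20, J45.21, J45.22, J45.90\*, J45.99\*) will be defined as either 1 inpatient claim or 2 outpatient events 30-365 days apart".

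Section 9.7.2, item 4, gives the purpose: patients with an asthma diagnosis "will be excluded to restrict to patients with only COPD".

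Annex 4 contains no separate asthma measure. It does contain a fuller J45 list under the respiratory-hospitalization covariate, with entries such as "J45.30', 'J45.31', 'J45.32" and the corresponding J45.4 and J45.5 codes.

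**The concern.** An exclusion criterion decides who is in the primary cohort. Here its reach depends on the coding system used when the asthma was recorded. Any 493 code counts, but only part of J45 does. A patient admitted once with J45.40, or seen repeatedly as an outpatient under J45.50, has coded asthma and is not excluded by the written rule.

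The protocol also treats the same claim in two ways. An admission in the baseline period with J45.40 as principal diagnosis counts as a respiratory hospitalization under Annex 4. Yet it does not trigger the asthma exclusion, for which one inpatient claim is enough.

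At stake is whether the primary result describes the population that Section 9.7.2 says it describes. Asthma itself is neither a covariate in Section 9.3.3 nor a row in Table 2. Retained asthma patients would therefore not be matched on asthma directly, and the balance tables would not show how many there are.

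**Working it through.** The plan gives no figure for this point, so there is none to reproduce. The check compares two code sets.

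**Inputs**
- Exclusion list (Section 9.2.2): J45, J45.20, J45.21, J45.22, `J45.90*`, `J45.99*`. An asterisk is read as a wildcard; a code without one is read as an exact match.
- Reference list (Annex 4, respiratory-hospitalization measure): 25 J45 entries, made up of 17 fully specified codes and 8 category headers.

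**Fully specified codes**

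| Group | Codes in Annex 4 | Covered by 9.2.2 | Missed |
|---|---|---|---|
| J45.2x | .20, .21, .22 | 3 | 0 |
| J45.3x | .30, .31, .32 | 0 | 3 |
| J45.4x | .40, .41, .42 | 0 | 3 |
| J45.5x | .50, .51, .52 | 0 | 3 |
| J45.90x | .901, .902, .909 | 3 | 0 |
| J45.99x | .991, .998 | 2 | 0 |
| Total | 17 | 8 | 9 |

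Share of fully specified codes missed: 9 / 17 = 53%.

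**Counting headers as well.** The 8 headers are J45, J45.2, J45.3, J45.4, J45.5, J45.9, J45.90 and J45.99. The exclusion covers 3 of them (J45, J45.90, J45.99). Covered in all: 8 + 3 = 11 of 25. Missed: 9 + 5 = 14.

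**Does the bare J45 cover the rest?** If it meant the whole family, nothing would be missed. The notation in Section 9.2.2 points the other way. Families carry an asterisk there (`491.*`, `492.*`, `496.*`, `J42.*`, `493.*`, `J45.90*`, `J45.99*`), and other codes are written out singly, as in the J44 and C34 lists. If J45 were a prefix, the five entries after it would add nothing.

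**Who stays in.** The rule needs one inpatient claim or two outpatient events 30 to 365 days apart. Patients retained are those who satisfy it only if J45.3x to J45.5x codes are counted. That includes mixed histories: one visit under J45.909 and several under J45.40 make only one qualifying outpatient event. Anyone who qualifies through a 493 code (data go back to 1 January 2008) or through listed J45 codes alone is still excluded.

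**The case against.** The best argument for the text is that a bare header may have been meant as a family. Notation in Annex 4 is not uniform. The list for diabetes without complications uses E11.0 and E11.6, where the Type 2 list gives E11.00, E11.01 and E11.618. Exertional breathlessness pairs `R06.0*` with a bare 786.0. Headers often stand beside their own subcodes, so redundancy alone does not settle the meaning. This stands to the extent that the intention may have been correct. But a programmer following Section 9.2.2 would most naturally treat J45 as an exact code, so the line needs correcting on either reading.

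Sections 9.8 and 9.12 allow documented changes to measure definitions and promise medical review of code lists before implementation. That is a route to a correction, not the correction itself.

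Four stronger readings are tempting and are not supported:
- **Biased hazard ratio.** The same list applies to both exposure groups, and nothing in the documents shows that these patients would be distributed differently between them after matching.
- **Wholly unadjusted asthma.** Correlates are in the propensity score and in Table 2: respiratory hospitalization (whose definition includes the missed codes), ICS, LABA/ICS, allergic rhinitis and year of cohort entry.
- **A patient count.** Any percentage of patients would be invented, and the 14,751 in Section 9.5 is a count of patients who had already met the selection criteria.
- **Sensitivity analysis 4 defeated.** Section 9.7.2 gives its aim as a larger sample, not mainly a contrast with and without asthma. It may indicate how the estimate behaves when more asthma-coded patients are admitted. It does not repair the primary cohort, because it drops the exclusion altogether.

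**Conclusion.** The point holds as a defect in the definition of the primary population. Read in its own notation, the ICD-10 list in Section 9.2.2 leaves out J45.3x, J45.4x and J45.5x. No other section supplies an asthma definition, and the stated aim of a COPD-only cohort is not met.

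The size is known only in codes: 9 of 17 fully specified J45 codes are missed, while the J45.90 and J45.99 groups are covered. The documents give no claims or patients by asthma code, so the number retained could be small or not.

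The conclusion rests on one reading, that J45 without an asterisk is an exact code; under a prefix reading only the wording is at fault. It is also unknown which list produced the 14,751, so that count may or may not be affected. The correction is worth making before analysis because it decides who enters the primary cohort.

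**What to change.** In Section 9.2.2, replace the ICD-10 asthma list with `J45.*`, matching the breadth of `493.*`. That entry captures all 25 J45 entries in Annex 4, against 11 as written. Confirm which list was used for the feasibility count of 14,751 (3,889 + 10,862). Rerun the asthma row of Table 1, and update the Abstract and Section 9.5 if the counts change. Record the change as an amendment, as Section 9.8 requires.

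The cost is one code-list edit and a rerun of cohort selection. The downside is a slightly smaller primary cohort if the narrower list was the one applied.
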